9.2 Sample Size and Accrual Rate

Approximately 135 eligible subjects will be enrolled in this multicenter clinical trial that will be conducted at approximately 25 UPMC sites and up to 5 external sites in North America.

The first primary objective is to demonstrate that TORS with de-escalation RT (50Gy) and Nivolumab is equivalent (not inferior) to the standard of care of chemotherapy + standard 60-66 Gy radiation. The first primary endpoint is probability of progression free survival where an event is any type of disease progression or recurrence (local, regional or distant). In this definition deaths from other cancers, other non-cancer causes or treatment related deaths are censored. The historical control for the study is based part upon the results of Huang ⁹ in which the probability of 3 year OS was approximately 65% for high risk (Group III, T4 or N3, age < 70) HPV+ patients treated with chemoradiation and that 3 year OS is an approximation of two year PFS. Since there is not an ideal, published cohort to use, the trial is designed to investigate whether TORS with 50 Gy RT + Nivolumab is not inferior to standard of care chemotherapy + standard 60-66 Gy radiation.

We plan to devote 2 years of accrual and one year of additional follow-up. We assume that the experimental arm is not inferior to the standard if the 2-year PFS is not less than 55%, 10% less than the assumed standard. Thus 55% 2-year TTP for de-escalation RT + Nivolumab is considered not inferior to the 65% 2-year PFS for Cisplatin + 60-66 Gy RT.

Using a one-tailed exponential test (using the maximum likelihood estimator for the hazard rate of the exponential distribution) at $\alpha = .10$, 135 patients will provide 90% power to reject the null hypothesis that the experimental arm is inferior (less than 55% 2-year PFS) when the underlying 2-year PFS is 65%.

The second primary objective is to demonstrate reduction in feeding tube dependence. We will compare 1-year PEG tube dependence for patients who have not progressed to the SOC. Based on

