unpublished results from RTOG 0234 for 84 patients treated with RT + cisplatin + cetuximab, 67 (80%) did not have disease progression at one year. Of these, 11 (16%) were dependent upon a feeding tube one year after the start of treatment. Assuming a 15% PEG tube SOC rate, we wish to demonstrate a 50% improvement or to 7.5% due to the proposed de-escalation regimen. We assume the same 1 year non-progression rate of 80% which suggests 80% of 135 or 108 patients will be candidates for a feeding tube at one year. A one tailed exact binomial test with 108 patients at alpha = .06 will have 80% power to detect a reduction in 1 year PEG tube rate from 15% to 7.5%. Using the Bonferroni inequality, the type I error for testing both primary hypotheses is 16% with 135 patients.

Thus, we require accrual of 45 patients/yr for 3 years (135 total) with one year of additional follow-up.

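### The 80% power for the PEG co-primary is right for exactly 108 evaluable patients, but averaged over the random evaluable number it is about 77%

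*Combined protocol and SAP*

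**What the plan says.** Section 9.2 of the combined protocol and SAP restricts the PEG comparison to patients who have not progressed. It takes a one-year non-progression rate of 80% from an earlier trial's unpublished data (67 of 84 patients) and concludes that "80% of 135 or 108 patients will be candidates for a feeding tube at one year". The null rate is set by "Assuming a 15% PEG tube SOC rate", and the target by "we wish to demonstrate a 50% improvement or to 7.5% due to the proposed de-escalation regimen". The power claim is that "A one tailed exact binomial test with 108 patients at alpha = .06 will have 80% power" for that difference.

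The plan enrols 135 patients in total. It gives no rejection cut-off, no rule for an evaluable number other than 108, and no allowance for variation in that number or for missing tube status.

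**The concern.** The denominator of this endpoint is an outcome of the trial: however many of the 135 patients are progression-free at one year. The power statement treats its expected value as a fixed sample size.

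With an exact binomial test this matters more than usual, because power does not rise smoothly with n. It falls slowly while the cut-off stays the same, then jumps when the cut-off rises by one. One such jump lies between 107 and 108, so the plan quotes power at a favourable point of the sawtooth.

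At stake is the stated power of one of two primary endpoints, in a trial that Section 9.1 describes as powered to give a definitive result.

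**Working it through.** **Inputs, all from Section 9.2.** Null rate 0.15; alternative 0.075; one-sided exact binomial test with alpha .06; total N = 135; one-year non-progression rate 0.80.

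**Rule.** For each evaluable number n, the cut-off c(n) is the largest c with P(X ≤ c | n, 0.15) ≤ 0.06. Power is P(X ≤ c(n) | n, 0.075).

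**Step 1: the plan's own figure.** 0.80 × 135 = 108. At n = 108, c = 10, exact alpha is 0.0559 and power is 0.8135. The stated 80% is reproduced.

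**Step 2: other values of n.**

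| Evaluable n | Cut-off | Exact alpha | Power |
|---|---|---|---|
| 99 | 9 | 0.0595 | 0.792 |
| 107 | 9 | 0.0314 | 0.718 |
| 108 | 10 | 0.0559 | 0.814 |
| 109 | 10 | 0.0519 | 0.806 |
| 110 | 10 | 0.0481 | 0.798 |
| 115 | 10 | 0.0326 | 0.756 |
| 116 | 11 | 0.0564 | 0.839 |
| 121 | 11 | 0.0390 | 0.803 |
| 123 | 11 | 0.0335 | 0.788 |
| 124 | 12 | 0.0567 | 0.861 |

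From n = 90 to 115, power reaches 80% only at 108 and 109. It reaches 80% again at 116 to 121 and at every n from 124 to 135.

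**Step 3: average over the evaluable number.** With n ~ Binomial(135, 0.80), whose central 95% range is 99 to 117:

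- Average power = Σ P(n) × power(n) = 0.771. Average exact alpha, computed the same way, is 0.043.
- P(n < 108) = 0.449.
- P(n = 108 or 109) = 0.170, and P(n = 116 to 121, or n ≥ 124) = 0.048. The chance of power of at least 80% is their sum, 0.219 before rounding of the parts. The chance of power below 80% is 1 − 0.219 = 0.781.

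**Step 4: is 80% non-progression consistent with the rest of the plan?** The PFS alternative in Section 9.2 is 65% at two years under an exponential model, which gives √0.65 = 0.806 at one year. Average power at that rate is 0.774, so the result does not come from a pessimistic input.

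**Step 5: sensitivity to how .06 is read.** At n = 107, a cut-off of 10 has exact alpha 0.0603 and power 0.821. Accepting it removes the drop at 107. If .06 is read as a rounded value (exact alpha below 0.065), average power is 0.791.

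**Step 6: sensitivity to the evaluable fraction (assumed values, strict ceiling).**

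| Case | Average power |
|---|---|
| Non-progression 75% | 0.748 |
| Non-progression 80%, 5% of tube status missing (0.80 × 0.95 = 0.76) | 0.753 |
| Non-progression 80% (plan) | 0.771 |
| Non-progression 85% | 0.796 |
| Non-progression 90% | 0.819 |

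The 5% missing rate is not in the documents and serves only as an illustration.

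**The case against.** The strongest reply is that nothing in the plan is miscalculated. The power statement is conditional on 108 patients and correct on that condition. The plan openly derives 108 as 80% of 135, and powering at the expected evaluable number is common practice. This stands: a reader might infer that the 80% is an arithmetic error, and the documents do not support that.

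A reader might also infer that 80% power is available only if exactly 108 or 109 patients are evaluable. That goes too far, since power also reaches 80% at 116 to 121 and from 124 up. Those values have a combined probability of only about 5% under the plan's assumptions, so they hardly move the average.

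The drop to 72% at n = 107 is fragile as well. It turns on 0.0003 of alpha, and the plan prints alpha to two decimals. This also stands, and it is why the average is the better summary. A strict ceiling is the ordinary meaning of an exact test at a given level, but the plan does not say so. With 107 evaluable patients and 10 of them tube-dependent, the two readings give opposite decisions.

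Finally, the plan does provide for collecting tube status: Section 9.6 tracks it at every patient-reported-outcome visit, and Section 5.5 includes a 12-month visit. The missing-data case is therefore a sensitivity check, not evidence of a shortfall.

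**Conclusion.** The point holds as a minor one. Under the plan's own rates and a strict .06 ceiling, the 135-patient design gives about 77% power for the PEG endpoint on average, against a stated 80%. The chance that the realised evaluable number gives power below 80% is about 78%.

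The result rests on three assumptions: independent patients with an 80% non-progression rate, complete tube status, and exact alpha at or below .06. The shortfall narrows to about 1 point if .06 is taken as rounded. It all but closes at 85% non-progression and is gone at 90%; at 75% it widens to about 5 points. False-positive risk is not the issue, because average alpha is below the nominal level.

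**What to change.** In Section 9.2, restate the PEG power as about 77% averaged over the number of evaluable patients, and as 81% if exactly 108 are evaluable. Add one sentence saying that exact alpha may not exceed .06 and that the cut-off is set by the realised evaluable number. A short table of cut-offs by n would be convenient but is optional, because a strict exact test already fixes each one.

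The cost is a slightly less favourable stated figure. No extra patients are needed. If the sponsor preferred to keep 80% as the average under the strict ceiling, total enrolment would have to be about 145, but this point does not ask for that.

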9.3 Secondary Objectives

Secondary endpoints include toxicity, recurrence patterns, overall survival, swallowing function, and patient-reported outcomes.

Toxicity. For each arm, all treated patients will be evaluated by CTCAE version 4.0. Descriptive statistics will be provided by grade and type of toxicity.). The proportion of radiation-attributable grade III/IV toxicities will be estimated with 95% confidence intervals. These confidence intervals will be informally compared to published rates for standard of care radiation. In addition, frequencies of toxicity by grade in each arm will be compared with the Jonckheere-Terstra test

Recurrence Patterns Kaplan-Meier estimates with confidence intervals will be prepared for local, regional and distant recurrence. In addition, cumulative incidence functions will be estimated for local, regional and distant recurrence as well as death in the absence of disease progression. Gray's test will be applied to test differences in cumulative incidence patterns between treatment arms.

Overall Survival. Overall survival will be determined as the time from registration onto the study until death from any cause. Patients who were alive at the time of analysis will be censored at the date last known alive. Kaplan-Meier estimates will be calculated, along with their corresponding 95% confidence intervals. The median, 1-year, and 2-year survival rates will be estimated. Only eligible and treated patients will be analyzed for overall survival (by arm).

Swallowing Function and Voice. Descriptive statistics will be provided with confidence intervals for swallowing function, evaluated using the MBS ratings, PSS-HN normalcy of diet scale, and the validated survey MDADI instrument. Longitudinal analysis will be performed on each of these measures. All eligible and treated patients (on both steps) will be analyzed for PSS-HN diet scale, MDADI, and VHI-10. The MBS analysis will be performed on eligible and treated patients only if accrued at vetted participating centers.

Quality of Life. The primary variable of interest in the QOL analysis is the individual change in the FACT-H&N total score from baseline (prior to TOS) to 6 months post-RT. The within-patient change in FACT_H&N score will be calculated and tested with the signed rank test or Friedman's test for more than 2 sequential observations per patient.

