2.1 Primary Objective

The dual primary objectives of the study are (1) to test the hypothesis that the proposed adjuvant de-escalation strategy (TORS + 50Gy RT + Nivolumab cancer) is equivalent (non-inferior) to current standard of care cisplatin chemotherapy + standard 60-66 Gy radiation, and (2) to demonstrate a reduction in the rate of PEG tube dependence at one year.

Primary Hypotheses: We hypothesize that HPV + OPC is a distinct immunologic disease with a more favorable prognosis compared to HPV- OPC and represents a novel opportunity for de-escalation strategies in the adjuvant setting in Intermediate-Risk p16+ OPC groups after trans-oral resection (TORS). Risk-Adaptive de-escalation through a combination of TORS surgical resection followed by de-escalated RT (50 Gy accelerated fractionation) and concurrent Nivolumab immunotherapy in HPV+ OPC patients will result in similar PFS compared to historical results of standard CRT studies (60-66 Gy +/- Cisplatin) in the adjuvant setting, typically recommended for Intermediate and High Risk patients (HPV-, >4 metastatic nodes, + extensive ENE, + margins), as well as improvement in secondary endpoints of reduced toxicity, and patient QOL measures.

We further hypothesize that RT combined with concurrent and adjuvant Nivolumab will offer similar PFS outcomes to historical trials using cisplatin-based CRT through reduced tumor microenvironment immune suppression, enhanced systemic immune activation and response, and reduced toxicity by eliminating standard chemotherapy and allowing de-escalated RT.

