The purpose of this phase II trial of p16⁺ OPSCC patients that will undergo transoral surgery followed by de-intensified adjuvant radiotherapy plus nivolumab is to demonstrate equivalent oncologic outcome with fewer adverse effects and improved quality of life when compared to the standard of care

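### The only toxicity comparison with published rates counts radiation-attributable grade III/IV events, so it cannot support fewer adverse effects than cisplatin-radiotherapy for the whole regimen

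*Combined protocol and SAP*

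**What the plan says.** The opening of Section 9 states the purpose as "equivalent oncologic outcome with fewer adverse effects and improved quality of life when compared to the standard of care". Section 2.1 identifies that standard as "current standard of care cisplatin chemotherapy + standard 60-66 Gy radiation" and expects toxicity to fall because chemotherapy is dropped and the radiation dose is lowered. The claim is therefore about a whole regimen, in which nivolumab takes the place of cisplatin.

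The Toxicity paragraph of Section 9.3 plans three things:

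- For all treated patients, graded by CTCAE: "Descriptive statistics will be provided by grade and type of toxicity".
- One estimate with an interval and an outside benchmark: "The proportion of radiation-attributable grade III/IV toxicities will be estimated with 95% confidence intervals". Then: "These confidence intervals will be informally compared to published rates for standard of care radiation".
- A test: "frequencies of toxicity by grade in each arm will be compared with the Jonckheere-Terstra test".

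No source, expected rate or time window is given for the published rates, and no decision rule is attached to the comparison.

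**The concern.** The aim concerns radiation plus nine doses of nivolumab against cisplatin plus 60-66 Gy. The one quantity placed beside published figures covers only the radiation part of the new regimen, and only grades III and IV. A severe event attributed solely to nivolumab does not enter it, and neither does a fatal event of any attribution. If this figure is later cited in support of fewer adverse effects, the reader will be comparing part of one regimen with an undefined part of another.

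**Working it through.** **Step 1. Does another planned analysis make the whole-regimen comparison?**

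- *Descriptive tables (9.3).* These cover all toxicity, but no interval or external benchmark is planned.
- *Between-arm test (9.3).* Section 9.1 describes a single-arm trial, so there is no second arm and the test cannot be run.
- *DLT monitoring (9.4, Safety Monitoring).* This counts nivolumab-related events only if they are grade 3 or above and do not resolve to grade 1 within 28 days, or if they delay radiotherapy by more than 2 weeks or prevent its completion. The benchmarks are internal (25% acceptable, 40% excessive). The window closes 4 weeks after radiotherapy, whereas Section 5.2 gives six adjuvant doses every 4 weeks, starting in the second or third week after radiotherapy. Most of those doses fall after the window.
- *Deaths.* Treatment-related deaths are censored in the first primary endpoint (9.2). They count in overall survival and in the cumulative incidence of death without progression (9.3), but neither is a toxicity comparison.

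None of these fills the gap.

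**Step 2. Is the radiation-attributable count well defined?** The attribution scale in Section 5.3 relates an event to protocol treatment as a whole. No rule is given for separating radiation from nivolumab.

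**Step 3. How large could the omitted part be?** The plan states no toxicity rate or precision target, so there is no figure to reproduce. What follows is an illustration of scale.

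Inputs:

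- Nivolumab-related grade 3-4 rate, pN: 24/268 = 9.0% and 52/306 = 17.0% (Section 1.5, nivolumab safety in the metastatic setting).
- Radiation-attributable grade III/IV rate, pR: not in the documents; assumed 20-40%, per patient.
- n = 135 (Section 9.2), taking all as treated.

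Under independence, the any-treatment rate is 1 - (1 - pR)(1 - pN) = pR + pN(1 - pR). For example, 0.30 + 0.09 × 0.70 = 0.363 and 0.30 + 0.17 × 0.70 = 0.419.

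| pR (assumed) | Exact 95% CI for pR | Any-treatment rate, pN = 9.0% | Any-treatment rate, pN = 17.0% |
|---|---|---|---|
| 20% (27/135) | 13.6-27.7% | 27.2% (+7.2) | 33.6% (+13.6) |
| 30% (40/135) | 22.1-38.1% | 36.3% (+6.3) | 41.9% (+11.9) |
| 40% (54/135) | 31.7-48.8% | 45.4% (+5.4) | 50.2% (+10.2) |

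The approximate half-width at 30% is 1.96 × √(0.3 × 0.7/135) = 0.077, about 8 points.

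At 17.0% the any-treatment rate lies above the whole interval for the radiation-only rate in all three rows; at 9.0% it stays inside. If pR is 50-60%, it stays inside at 17.0% as well (58.5% against an upper limit of 59.1%; 66.8% against 68.3%). Without independence, the addition is at most 9 or 17 points (events in different patients) and could be nil (every nivolumab event in a patient already counted).

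**Step 4. Grade 5.** Section 1.5 reports 3 drug-related deaths among 306 patients. At that rate, 135 × 3/306 = 1.3 deaths would be expected here, and none would enter a grade III/IV count.

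**Step 5. Which way does the comparison lean?** The trial's side can only be lowered by leaving events out. The other side depends on the published rates:

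- If they count all toxicity of cisplatin plus radiotherapy, the comparison favours the new regimen.
- If they are radiation-only or radiation-attributable, cisplatin toxicity is left out too. The net direction is then unknown, and the whole-regimen question is not addressed.

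**The case against.** The strongest reply is that Section 9.3 compares like with like: radiation-attributable events with rates for standard-of-care radiation. That suits a stated secondary objective in Section 2.2, which concerns toxicity at different doses of postoperative radiotherapy. The comparison is also "informally compared to published rates for standard of care radiation", with no threshold, and Section 9.1 rests the benefit of de-escalation on feeding-tube dependence, a co-primary endpoint with its own test. Nothing names the toxicity comparison as the test of fewer adverse effects.

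Much of this stands. A reader might infer that the comparison is biased in favour of the regimen. The documents do not support that as a flat statement, because the published rates are not identified and the direction turns on them. A reader might also infer that nivolumab toxicity and deaths are left out of the trial's reporting. They are not: the descriptive tables, DLT monitoring, overall survival and death without progression all capture some or all of them.

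The figures are also open to challenge. The radiation rate and independence are assumptions. The 17.0% comes from a phase 1 study across 0.1-10 mg/kg with therapy for up to 2 years, and the 9.0% from previously treated advanced melanoma. The any-treatment rate is a different quantity, not a corrected radiation rate, and no matching shift on the comparator side can be computed from the documents.

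What the reply does not remove is the mismatch with the aim in Section 9. A radiation-only comparison is reasonable for the dose question, but the plan has no runnable comparison for the regimen question.

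**Conclusion.** The point holds as a gap in scope and specification. The single runnable external toxicity comparison excludes nivolumab-only and grade 5 events, so it cannot support fewer adverse effects than cisplatin plus 60-66 Gy for the regimen as a whole. This is so whichever way the published rates are defined; only the direction of any bias depends on them.

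The illustrated omission of about 5-14 points is comparable to or larger than the sampling uncertainty. It is an indication of scale under assumed inputs, not an estimate of bias. The primary analyses are unaffected, and the change is a worthwhile improvement to a secondary one.

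**What to change.** In Section 9.3:

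1. Estimate, with 95% CI, the proportion of patients with any treatment-related (radiation or nivolumab) grade 3-5 event, and the proportion with any all-cause grade 3-5 event, through the adjuvant nivolumab phase.
2. Compare both informally with named published rates for cisplatin plus 60-66 Gy, matched as closely as possible on attribution rule and time window, and state any mismatch.
3. Keep the radiation-attributable grade III/IV rate as a supportive analysis for the radiation-dose question.
4. Delete the between-arm test.

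The cost is mainly wording. The attribution scale in Section 5.3 already relates events to protocol treatment as a whole, and the schedule in Section 7 has adverse event evaluation during adjuvant nivolumab and at end of treatment. The downsides are that the toxicity figure may be less favourable and that a closely matched published rate may not exist; if so, the report should say so.

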5.5 Supportive care and Other Assessments

Patient Reported Outcomes (PROs)

Quality of Life (QOL) assessments will be performed at baseline, end of treatment, and at 3, 6, 12, and 24 months after completion of treatment. If an additional tumor assessment is done prior to 3 years from study entry, one final QOL assessment is requested. QOL will continue to be collected for all patients post recurrence.

Paper questionnaires will be completed by the patient, and then data from the questionnaire should be provided within 7 days of completion. The original copy needs to be kept in the study subject's research binder.

Rehabilitation

It is strongly encouraged that all patients be referred for an assessment by a certified physical therapist after the completion of concurrent therapy. Components of the evaluation should include: neck shoulder and jaw range of motion, general conditioning level, the degree of treatment related fatigue, and postural issues. Patients with significant levels of deconditioning, postural abnormalities, or decrease in range of motion may require physical therapy. Occupational therapy may be needed in patients with extreme degrees of dysfunction. Patients with lymphedema should be referred for lymphedema therapy which should include: education, manual lymph drainage and the use of compression garments.

Speech and Language Pathology

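### For FACT-H&N at more than two time points the plan names only Friedman's test, which uses complete cases and gives no estimate, and no confidence interval is planned for the 6-month change

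*Combined protocol and SAP*

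**What the plan says.** The FACT-H&N analysis is the Quality of Life paragraph of section 9.3. Its main variable is "the individual change in the FACT-H&N total score from baseline (prior to TOS) to 6 months post-RT". It then says "The within-patient change in FACT_H&N score will be calculated", and that this is tested with the signed-rank test or with Friedman's "test for more than 2 sequential observations per patient". Nothing more is specified: no summary statistic, interval, model, list of visits or handling of missing forms.

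Section 5.5 schedules the assessments: they are "performed at baseline, end of treatment, and at 3, 6, 12, and 24 months after completion of treatment". It adds that "QOL will continue to be collected for all patients post recurrence". That is six nominal forms. Footnote 10 to the section 7 schedule places the end-of-treatment visit at the 6-month scan after radiotherapy, which leaves five distinct time points.

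Elsewhere in section 9.3, confidence intervals are planned for toxicity, recurrence, overall survival and the swallowing measures, and a longitudinal analysis is planned for the swallowing measures, including MDADI. Neither is planned for FACT-H&N.

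**The concern.** A patient followed on schedule has more than two observations, so the method that applies to the full series is Friedman's test. Two consequences follow without any assumed figure.

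- **Complete blocks.** The standard test ranks scores within a patient and needs every included visit. One missing form removes that patient's other forms as well. If month 24 is included, a patient who dies earlier contributes nothing, not even valid 3- and 6-month forms. Forms collected after recurrence are lost too whenever any other included form is missing.
- **No estimate.** The test says whether scores differ somewhere across visits. It does not say when, in which direction or by how much.

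The second point matters most in this design. The opening of section 9 and section 9.1 state an aim of better quality of life than under standard care. With a single arm, any such comparison is with outside data and needs an estimated change with its uncertainty. A p-value for change over time cannot be set against a published figure.

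**Working it through.** The plan gives no FACT-H&N sample size, power, completion rate or expected loss, so it has no figure of its own to reproduce.

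**Inputs.** N = 135 (section 9.2: "Approximately 135 eligible subjects will be enrolled"). Number of forms k = 5 distinct or 6 nominal (sections 5.5 and 7). Completion per form r is not stated; 95% and 90% are assumptions, with a wider range below.

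**1. Patients usable in Friedman's test, independent missingness.** Share = r^k.

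| Forms included | r = 95% | r = 90% |
|---|---|---|
| 3 (baseline, months 3 and 6) | 0.95^3 = 85.7% (116) | 0.90^3 = 72.9% (98) |
| 5 distinct | 0.95^5 = 77.4% (104) | 0.90^5 = 59.0% (80) |
| 6 nominal | 0.95^6 = 73.5% (99) | 0.90^6 = 53.1% (72) |

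Over a wider range, five forms leave 90.4% at r = 98%, 44.4% at 85% and 32.8% at 80%.

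**2. The two-point signed-rank test.** Share = r^2: 90.2% (122 patients) at r = 95% and 81.0% (109) at r = 90%. This comparison is much less exposed.

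**3. Clustered missingness.** Let completion vary between patients by a beta distribution with mean r and intraclass correlation ρ. With s = 1/ρ − 1 and a = r·s, the share with all k forms is the product over i = 0 to k−1 of (a + i)/(s + i). For six forms, r = 95% and ρ = 0.3: s = 2.333, a = 2.217, and the product is 0.950 × 0.965 × 0.973 × 0.978 × 0.982 × 0.984 = 84.3%. With ρ = 0.5 it is 88.3%. At r = 90% the shares are 70.6% and 77.7%. The loss is therefore 12% to 16% at r = 95% and 22% to 29% at r = 90%, against 26% and 47% when missingness is independent.

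**4. Deaths before month 24.** The only survival figure usable here is the historical control in section 9.2, 65% at 3 years. If survival is exponential (assumption), 2-year survival is 0.65^(2/3) = 75.0%. That control is a T4 or N3 chemoradiation group, so the figure is a rough guide and may be pessimistic for this population. Five forms then leave 0.750 × 0.774 = 58% at r = 95% and 0.750 × 0.590 = 44% at r = 90%. Six forms leave 55% and 40%.

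**5. Month-24 forms not yet due.** Section 9.2 gives accrual as 2 years in one place and 3 years in another, each with 1 further year. With uniform accrual, analysis at the end of that period, and 0 to 2 months from registration to the end of radiotherapy, the month-24 form has fallen due for (48 − 24 − lag)/36 = 67% to 61% of patients with 3 + 1 years, and for (36 − 24 − lag)/24 = 50% to 42% with 2 + 1 years. The plan does not say when the quality-of-life analysis is done.

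**6. What a likelihood model keeps.** Patients with a baseline and at least one later form, five forms, independent missingness, no deaths: 0.95 × (1 − 0.05^4) = 95% (128) at r = 95% and 0.90 × (1 − 0.10^4) = 90% (121) at r = 90%, against 104 and 80 in step 1. Entering baseline as a response also keeps patients who have only later forms.

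**The case against.** The strongest reply is that the main variable is a two-point change, that the plan already names a suitable test for it, and that the change is calculated for each patient. This stands. The plan can produce a 6-month result, and Friedman's test does not govern it. What is missing there is a planned summary with an interval.

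The visits entering Friedman's test are not stated either, so the test could stop at month 6 and lose fewer patients. This also stands, and it is why the loss is given as a range. Stopping early would still leave the result without an estimate.

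FACT-H&N is secondary, and section 9.1 carries the formal quality-of-life hypothesis through feeding-tube status. That limits the weight of the point but not its substance, since the remedy costs little.

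Stronger readings are tempting, and the documents do not support them:

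- A reader might infer that a third or more of patients will be lost. With five independent forms this needs completion at or below 92.2% per form (0.922^5 = 0.667), and the documents give no completion rate.
- A reader might turn the loss into a wider standard error for the 6-month change. That change needs two forms rather than five, Friedman's test has no standard error of a mean, and no standard deviation is given.
- A reader might infer that recurrence removes patients. Section 5.5 continues collection after recurrence; only a missing form removes them.
- A reader might extend the point to MDADI, but intervals and a longitudinal analysis are already planned for it.

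**Conclusion.** The point holds in a limited form. For more than two time points the named method uses complete cases and gives no estimate; for the 6-month change a test is named but no interval. Both follow from the text alone.

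The size of the loss rests on assumptions. With independent missingness and 95% or 90% completion per form, 77% or 59% of patients remain with five forms, and 74% or 53% with six. Clustered missingness or fewer visits make the loss smaller; deaths before month 24 or an analysis before that form is due make it larger. The co-primary analyses are not affected.

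**What to change.** In section 9.3, replace Friedman's test with a likelihood-based repeated-measures model for the FACT-H&N total score:

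- Visit as a categorical factor, with an unstructured covariance. Five visits need 5 × 6/2 = 15 covariance parameters, which about 135 patients should support.
- All available forms, including those after recurrence.
- Baseline as one of the repeated responses rather than a covariate. Section 9.3 sets baseline before transoral surgery, while section 4 allows registration up to 8 weeks after surgery, so pre-surgery forms may be absent for some patients. They would then still contribute their later forms.
- The 6-month change from baseline with its 95% confidence interval as the main quality-of-life estimate, and the other visits from the same model.
- The signed-rank test at 6 months as a supporting analysis.

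State which visits are included, how the end-of-treatment and 6-month forms are treated when they coincide, and when the analysis is done.

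The cost is SAP wording and standard software. The downside is small but real: the model assumes forms are missing at random and implicitly extends scores past death. So report the numbers dead and the numbers with missing forms at each visit, and add a sensitivity analysis, for example one that lowers unobserved scores by a range of fixed amounts.
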